5.6 Dose Limiting Toxicity (DLT) definition

Toxicity will be evaluated according to the NCI CTCAE, version 4.03. The DLT safety observation window is defined as the first 3 weeks (one cycle). A DLT will be defined as any of the following AEs, occurring within the first 21 days of dosing and considered possibly related (except where defined) to ONC201:

Hematologic:

- Grade 4 neutropenia that persists for >7 consecutive days
- Febrile neutropenia (defined as neutropenia \geq Grade 3 and a body temperature 38.5°C)
- Grade \geq 3 neutropenic infection
- Grade 4 thrombocytopenia (platelets $<25,000$ cells/mm 3) or Grade \geq 3 thrombocytopenia with bleeding

Nonhematologic:

- Any other Grade \geq 3 toxicity not classified under CTCAE blood or bone marrow with the exception of nausea, vomiting, or diarrhea. Grade 3 nausea or vomiting that persists for 5 days and is not controlled with standard antiemetic therapy will be considered a DLT.
- Alopecia is not a DLT
- Any AE leading to inability to complete planned study drug during the DLT window should be considered a DLT

Although toxicities may be observed at any point during treatment, only those occurring during the defined DLT observation window of treatment (1 cycle) that are considered DLTs will guide dose escalation decisions, expansion of a dose level, or evaluation of intermediate dose levels. Patients will be monitored through all cycles of therapy for treatment-related toxicities, and all toxicities, including those occurring in beyond the DLT observation window will be monitored.

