3.3 Dose and Planned Scheme

In Phase I, ONC201 is intended to be administered once every week at 375mg or 625mg. Dexamethasone will be administered same day of each ONC201 administration. One cycle is defined as 21 days (three weeks), which is also the dose-limiting toxicity (DLT) window.

Phase 1 of the study involves a 3 + 3 dose escalation with a starting dose of 375mg ONC201 followed by an escalation to 625mg ONC201. This will allow assessment of the safety, tolerability, pharmacodynamic effects, and efficacy of two doses of weekly ONC201 in combination with dexamethasone. Dexamethasone will be administered at 20mg weekly. In the unexpected event that >1/6 patients in the first cohort experience a DLT, dose de-escalation will proceed by a 3 + 3 design using 8mg dexamethasone and 375mg ONC201. Further dose de-escalation would involve step-wise decreasing 125mg increments of ONC201. Dose de-escalation below 125mg ONC201 and 8 mg dexamethasone will not be permitted.

Once a recommended phase 2 dose (RP2D) has been determined in Phase I based on a favorable benefit/risk ratio (anticipated to be 625mg ONC201 with 20mg dexamethasone), the study will progress to Phase 2 of the study.

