5.2 ONC201 Administration

Patients will receive 625 mg of ONC201 on an outpatient basis. The study drug, ONC201, will be supplied in capsule form for oral dosing. Patients should take designated capsules of ONC201 at approximately the same time on each day of drug administration. Patients will be instructed to not eat for 2 hours pre and 2 hours post dosing. If the patient vomits after taking ONC201, they should not retake the dose. Missed doses will not be made up.

ONC201 should be taken with a glass of water and consumed over as short a time as possible. Patients should swallow the capsules as a whole and not chew them. Do not crush or empty the capsule. If vomiting occurs during the course of treatment, no re-dosing of the patient is allowed before the next scheduled dose. The occurrence and frequency of any vomiting during a treatment cycle must be noted as an adverse event. In addition, on the days of drug administration the exact time of any episodes of vomiting within the first 4 hours post-dosing on that day must be noted whenever possible.

Dexamethasone will be obtained and administered per standard of care guidelines for multiple myeloma patients. Administration of dexamethasone is recommended approximately 6 hours (+ 2 hours) after ONC201.

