7.3 Treatment

ONC201 will be orally administered at 625mg weekly day 1, day 8, and day 15 of each treatment cycle (21 days). Dexamethasone will be administered at the indicated dose on each day that ONC201 is administered in each treatment cycle (day 1, day 8, and day 15). Administration of dexamethasone is recommended approximately 6 hours (+ 2 hours) after ONC201.

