9.7 Severity Assessment

If required on the adverse event case report forms, the investigator will use the following definitions of Severity in accordance with Cancer Therapy Evaluation Program, Common Terminology Criteria for Adverse Events (Version 4.03) to describe the maximum intensity of the adverse event. If the event is serious, the CTC grade reported in the adverse event CRF must be consistent with the description of CTC grade included in the narrative section of the serious adverse event report.

Table 8.1: General AE Grading Assessment

Grade	Clinical Description of Severity
0	No change from normal or reference range (This grade is not included in CTCAE but may be used in certain circumstances)
1	MILD adverse event
2	MODERATE adverse events
3	SEVERE adverse events
4	LIFE-THREATENING OR DISABLING adverse events
5	DEATH RELATED TO adverse events

Note the distinction between the severity and the seriousness of an adverse event. A severe event is not necessarily a serious event. For example, a headache may be severe (interferes significantly with patient's usual function) but would not be classified as serious unless it met one of the criteria for serious adverse events, listed above.

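### The DLT definition exempts nausea, vomiting and diarrhea with no upper grade, so Grade 4 vomiting or diarrhea that costs no Cycle 1 dose is, read literally, not a DLT

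*Combined protocol and SAP*

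**What the plan says.** Section 5.6 sets a 21-day DLT window and counts events possibly related to ONC201. For nonhematologic toxicity, Grade 3 or higher is a DLT, "with the exception of nausea, vomiting, or diarrhea. Grade 3 nausea or vomiting that persists for 5 days" and not controlled by standard antiemetics being the only specific route back in. Diarrhea has no route back in at any grade. There is one general clause: "Any AE leading to inability to complete planned study drug during the DLT window should be considered a DLT".

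The same section ties the count to the decision: "only those occurring during the defined DLT observation window of treatment (1 cycle) that are considered DLTs will guide dose escalation decisions". Section 3.3 describes a 3+3 scheme with a "starting dose of 375mg ONC201 followed by an escalation to 625mg ONC201", and de-escalation if ">1/6 patients in the first cohort experience a DLT".

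Four other places bear on a Grade 4 event:

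- Section 9.7, Table 8.1 defines Grade 4 as "LIFE-THREATENING OR DISABLING adverse events".
- Sections 5.5 and 7.6 call any drug-related Grade 4 event unacceptable and require withdrawal.
- Table 6.1 in Section 6 has one row for Grades 3 and 4 together. Dosing is held until below Grade 2 and, at the first instance, resumed at 500 mg ONC201 with 8 mg dexamethasone if this happens within 21 days.
- Section 5.2 states: "If the patient vomits after taking ONC201, they should not retake the dose. Missed doses will not be made up".

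**The concern.** The definition orders severity the wrong way round. Uncontrolled Grade 3 vomiting lasting 5 days is a DLT. Grade 4 vomiting, which the protocol's own table ranks higher, is not one by grade, and neither is Grade 4 diarrhea. The exemption was probably meant for Grade 3 events only, but the text does not say so.

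These toxicities are relevant to this drug. Section 1.2.3 reports emesis and loose feces in dogs, and Section 6 names nausea, vomiting and diarrhea among the attributable events that its dose rules cover.

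Because only events meeting the definition guide escalation, an uncounted Grade 4 event could let a dose level pass that would otherwise fail. The level chosen is then given to up to 30 evaluable Phase 2 patients (Section 3.2).

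**Working it through.** The plan gives no figure to reproduce. The check applies each criterion in Section 5.6 to one event and then looks at the effect on the count.

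**Inputs.** Doses on Days 1, 8 and 15 of a 21-day cycle (Section 7.3). DLT window of 21 days (Section 5.6). De-escalation limit of more than 1 in 6, stated for the first cohort (Section 3.3).

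**Step 1. Possibly related Grade 4 vomiting or diarrhea against the nonhematologic criteria**

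- Grade 3 or higher rule: exempt, because the exemption has no upper grade.
- Persistence add-back: not met as worded. It names Grade 3 only and omits diarrhea.
- Inability-to-complete clause: met if the Day 8 or Day 15 dose is lost. Otherwise not clearly met.

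**Step 2. The same event by timing and by which section is followed**

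| Grade 4 event | Sections 5.5/7.6 (withdraw) | Table 6.1 (hold, then resume) |
|---|---|---|
| Onset before the Day 15 dose, not recovered by the next dose | Dose lost: DLT | Dose lost: DLT |
| Onset before the Day 15 dose, below Grade 2 by the next dose | Remaining Cycle 1 doses lost: DLT | Possibly no dose lost: not clearly a DLT |
| Onset after the Day 15 dose, through Day 21 | No Cycle 1 dose left to lose: not a DLT as written | Same |

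The third row is the clear gap. The second row shows that the conflict between the withdrawal rule and Table 6.1 can change the count, so two sites could classify the same event differently.

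**Step 3. Calendar extent of the clear gap**

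Full days after the last Cycle 1 dose: 21 − 15 = 6. Share of the window: 6/21 = 0.286, about 29%, plus the rest of Day 15. This is a share of the calendar, not a probability of an event.

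**Step 4. Effect on the decision**

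Take a six-patient level that already has one DLT and add one such event.

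- As written: 1/6 = 16.7%, which does not exceed 1/6.
- If counted: 2/6 = 33.3%, which does.

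**Step 5. Table 6.1 and the starting cohort**

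The first resumption dose is 500 mg. From 625 mg this is a reduction of 625 − 500 = 125 mg. For the 375 mg cohort it would be an increase of 500 − 375 = 125 mg, so the row does not work as a reduction there.

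**The case against.** The strongest reply is that the gap is narrow and backstopped.

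- **Withdrawal plus the general clause.** If Sections 5.5 and 7.6 are followed, every drug-related Grade 4 event before the Day 15 dose costs a dose and becomes a DLT. This stands. It confines the clear gap to onset after the Day 15 dose, provided the sites do not follow Table 6.1 instead.
- **A broader reading of the general clause.** A 625 mg patient who resumes at 500 mg has not received the planned dose. A vomited Day 15 dose, which may not be retaken, might count as not completed. An event that ends treatment within the window might also qualify. Each reading is possible, but the text states none of them. The first does not help at 375 mg, and the second does not help with diarrhea.
- **Timing.** Sections 1.2.3 and 1.4 describe acute toxicity in nonclinical work as confined to the dosing day and short-lived, which makes Days 16 to 21 the less likely days. This is fair, and it is why the 29% must not be read as a risk. The evidence is nonclinical.
- **Rarity.** Section 1.3 reports no drug-related toxicity above Grade 1 in 10 evaluable patients dosed every three weeks, and no drug-related adverse events in 9 patients dosed weekly. This also stands, but all received single-agent ONC201 without protocol dexamethasone.
- **Backstops.** The Phase 2 dose is chosen on benefit and risk, serious events are reported promptly, all toxicities are monitored, and Section 10.3 has a discontinuation rule. An accompanying Grade 3 or higher nonhematologic event outside the exemption would still count. These limit the harm, but none makes the exempt event itself a DLT.
- **The Table 6.1 conflict is a general one.** It affects every drug-related Grade 4 event. However, other Grade 4 nonhematologic events are already DLTs by grade. For the exempt ones, the conflict can decide whether they are counted.

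**Conclusion.** The concern holds. As written, possibly related Grade 4 vomiting or diarrhea that costs no Cycle 1 dose is not a DLT, although the protocol elsewhere treats Grade 4 as life-threatening and unacceptable. The gap is clear after the Day 15 dose. It is ambiguous earlier in the cycle if Table 6.1 is followed.

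Its size can be stated only as a count: one event can separate 1/6 from 2/6 in a six-patient level. This assumes one DLT already in that level and no accompanying event that counts on its own. Section 3.3 states the limit for the first cohort; applying it to the 625 mg level assumes the usual 3+3 convention. The documents give no rate for these events, so the chance of a wrong escalation cannot be estimated and may be small. The change should be made because the rule, as stated, gives the wrong answer for a severe event and is cheap to correct.

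**What to change.** In Section 5.6:

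- Limit the exemption to Grade 3 nausea, vomiting or diarrhea.
- State that Grade 4 or higher vomiting or diarrhea possibly related to ONC201 within the 21-day window is a DLT, whether or not a dose is missed.
- Keep the 5-day add-back for Grade 3 nausea or vomiting, and leave the hematologic criteria unchanged.

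In Table 6.1, align the combined Grade 3 and 4 row with the mandatory Grade 4 withdrawal in Sections 5.5 and 7.6. A duration rule for Grade 3 diarrhea is optional and can be left to the sponsor.

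The cost is one or two sentences in Section 5.6 and one edit to Table 6.1. The downside is that a few events now exempt would count as DLTs and could slow escalation.

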6 DOSING DELAYS/DOSE MODIFICATIONS

The descriptions and grading scales found in the revised NCI Common Terminology Criteria for Adverse Events (CTCAE) version 4.0 will be utilized for dose delays and dose modifications.

Below are dose modifications (Table 6.1) for adverse events that are attributable to study drug, including: nausea, vomiting, diarrhea, neutropenia, and thrombocytopenia. If a patient

experiences other adverse events, or several adverse events and there are conflicting recommendations based on Grade, the investigator will use the recommended dose adjustment that reduces the dose. Dose modifications will be made based on an adverse event that occurs during any time during a cycle.

Criteria for disrupting treatment, dose modification, or discontinuation are listed in Table 6.1. Dose modifications are per the clinical judgment of the investigator and agreement of the subject, the treatment will be resumed according to the table below. Dose modification may not be required for adverse events that are clinically manageable.

Table 6.1 Dose adjustment rules for Adverse Events (AEs), including Nausea, Diarrhea, Neutropenia, Thrombocytopenia, and Other AEs. Alopecia does not require dose adjustments.

CTCAE Grade	Management/Next Dose for ONC201
≤ Grade 2	No change in dose
Grade 3 or 4*	Hold until < Grade 2. For first instance, if resolved to < Grade 2 within 21 days resume dosing at 500mg ONC201 and 8mg dexamethasone. For second instance, if resolved to < Grade 2 within 21 days resume dosing at 8mg dexamethasone and 375mg ONC201.**

*Patients requiring a delay of >21 days weeks should go off protocol therapy.

**Patients requiring > two dose reductions should go off protocol therapy.

Participants who experience an adverse event that requires a treatment delay or dose reduction should be monitored with appropriate laboratory testing or other clinical evaluation at least weekly until resolution; if the adverse event does not resolve within 21 days, the interval for testing may be reduced after consultation and written approval by the Overall Principal Investigator (or his designee).

For holds for reasons other than treatment related toxicities, if the participant does not meet criteria to resume treatment within 6 weeks of the event precipitating the hold, the study

agent(s) may be restarted with approval from the overall Principal Investigator or designee, as long as there has been no significant evidence of disease progression (e.g., by clinical findings, symptoms, tumor markers) during the treatment interruption.

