4.1 Inclusion

1. Patients must be refractory to, or not a candidate for, established therapy known to provide clinical benefit for their malignancy.
2. Measurable disease M protein component in serum (at least 0.5 g/dL) and/or urine (if present) (≥ 0.2 g excreted in a 24 hour collection sample), or serum free light chain level ≥ 10 mg/dL, provided the serum free light chain ratio was abnormal.
3. Able to swallow and retain oral medication.
4. All previous therapies for cancer, including radiotherapy, major surgery and investigational therapies must be discontinued for ≥ 14 days (≥ 28 days for mitomycin C or nitrosoureas) before study entry, and all acute effects of any prior therapy must have resolved to baseline severity or Grade ≤ 1 Common Terminology Criteria for Adverse Events (CTCAE v4.03), except alopecia or parameters defined in this eligibility list.
5. Age ≥ 18 years
6. ECOG performance status ≤ 1
7. Adequate organ and marrow function as defined below:
 - h. Absolute neutrophil count $\geq 1,000/\text{mm}^3$ without growth factor use ≤ 7 days prior to treatment (cycle 1 day 1, C1D1)
 - i. Platelets $\geq 50,000/\text{mm}^3$ without platelet transfusion ≤ 3 days prior to C1D1
 - j. Hemoglobin ≥ 8.0 mg/dL without red blood cell transfusion ≤ 3 days prior to C1D1
 - k. Total serum bilirubin $\leq 1.5 \times$ upper limit of normal (ULN) ; subjects with $>1.5 \times$ upper limit of normal require approval of medical monitor.
 - l. AST (SGOT)/ALT (SGPT) $\leq 2 \times$ ULN; $\leq 5 \times$ ULN if liver dysfunction is felt to be secondary to tumor burden
 - m. Serum creatinine $\leq 1.5 \times$ ULN (OR creatinine clearance ≥ 30 mL/min/1.73 m²)
 - n. Serum or urine pregnancy test (for females of childbearing potential) negative ≤ 7 days of starting treatment
8. Ability to understand and the willingness to sign a written informed consent document and comply with the study scheduled visits, treatment plans, laboratory tests and other procedures.
9. Female patients must be surgically sterile or be postmenopausal, or must agree to use effective contraception during the period of the trial and for at least 90 days after completion of treatment. Male patients must be surgically sterile or must agree to use effective contraception during the period of the trial and for at least 90 days after completion of treatment. The decision of effective contraception will be based on the judgment of the principal investigator or a designated associate.

CONFIDENTIAL

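### Blood counts may be Grade 2 at entry, but Table 6.1 lets a held patient resume only below Grade 2, so a patient back at the entry count can still go off therapy

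*Combined protocol and SAP*

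**What the plan says.** **Entry (Section 4.1).** Inclusion 7 sets floors of 1,000/mm³ for neutrophils, 50,000/mm³ for platelets and 8.0 for hemoglobin (printed in mg/dL). Inclusion 4 requires acute effects of earlier therapy to be back at baseline severity or at Grade 1 or lower, "except alopecia or parameters defined in this eligibility list". The listed counts are thus outside the Grade 1 limit.

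**During treatment (Section 6).** The grading scale is stated: "Common Terminology Criteria for Adverse Events (CTCAE) version 4.0 will be utilized for dose delays and dose modifications". Table 6.1 leaves the dose unchanged at Grade 2 or lower. For Grade 3 or 4 it reads "Hold until < Grade 2. For first instance, if resolved to < Grade 2 within 21 days resume dosing", at a reduced level. A footnote adds "Patients requiring a delay of >21 days weeks should go off protocol therapy" (one of the two time units is evidently stray). Section 6 nowhere refers to the patient's own baseline.

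**Related rules.** Section 5.5 withdraws a patient for any drug-related Grade 4 event, so the resumption path in practice concerns Grade 3. Section 7.3 doses on days 1, 8 and 15 of a 21-day cycle, and Section 5.2 does not replace missed doses. Section 10.1 requires at least two cycles, plus an on-study tumor assessment, for a patient to be evaluable for response. Section 10.3 reviews the study at 4 discontinuations in 12 patients, or 6 in 26, for treatment-related adverse events.

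**The concern.** The bar for going back on drug is higher than the bar for starting it. Table 6.1 also treats the same count in two ways: at Grade 2 with no earlier hold, dosing continues; at Grade 2 after a hold, dosing is barred. For a patient who entered at Grade 2, full recovery to the pre-treatment state never satisfies the table.

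Three things are at stake. Such a patient can lose protocol therapy without being worse than at entry. If the hold comes early, the patient drops out of the evaluable denominator for the primary endpoint instead of being counted as a non-responder. And Section 10.3 does not say whether the removal counts as a treatment-related discontinuation.

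**Working it through.** The plan gives no figure for this point. The check is a reading of the rules followed by a calendar trace.

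**1. Can a patient enter at Grade 2?** Let L be the lowest count that still grades as 1 for a given parameter. Entry counts from the inclusion 7 floor up to just below L are above Grade 1. The protocol prints no Grade 1 to 3 cut-offs; the only blood-count limit it gives is Grade 4 platelets below 25,000 (Section 5.6). So L is an assumption, with this range:
- L at or below the floor for all three counts: the gap disappears.
- L above the floor for at least one count (above 1,000, 50,000 or 8.0): the gap exists for that count, and widens as L rises.

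The inclusion 4 exemption supports the second case but does not prove it, because the list also contains chemistry parameters.

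**2. Calendar trace.** Dosing days are 1, 8, 15, 22, 29, 36 and so on. Assume a drug-attributable Grade 3 count, an actual hold, recovery to the patient's own entry grade in 3 to 7 days (3 days in the day 4 row), and a count that then stays there. Off therapy applies once the dosing day minus the event day exceeds 21.

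| Event found | Back at entry count | Grade 1 at entry | Grade 2 at entry |
|---|---|---|---|
| Day 8 | Day 11–15 | Misses 8; resumes 15 | Misses 8, 15, 22, 29; off therapy |
| Day 15 | Day 18–22 | Misses 15; resumes 22 | Misses 15, 22, 29, 36; off therapy |
| Day 4 (unscheduled count) | Day 7 | Misses none; resumes 8 | Misses 8, 15, 22; off therapy |

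For the day 8 hold, 29 − 8 = 21 is still within the limit and 36 − 8 = 28 is not. For day 4, 22 − 4 = 18 is within it and 29 − 4 = 25 is not. Within each row the two patients differ only in entry grade.

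**3. Evaluability.** Two cycles are 2 × 21 = 42 days and 2 × 3 = 6 doses. The 21-day allowance runs out on day 8 + 21 = 29 or day 15 + 21 = 36, both before day 42. These patients have had 1 of 6 and 2 of 6 doses. For a hold from day 22 the allowance ends on day 22 + 21 = 43. Whether that patient has received two cycles is unclear, because Section 10.1 does not say how held doses count.

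**4. Section 10.3.** Its stated operating characteristics reproduce. P(X ≥ 4 | n = 12) is 0.507 at 30% toxicity and 0.0022 at 5% (stated: 51% and 0.2%). Overall, P(X₁₂ ≥ 4) + Σ P(X₁₂ = x) · P(X₁₄ ≥ 6 − x), summed over x = 0 to 3, is 0.849 and 0.0033 (stated: 85% and 0.3%). Those figures are not in dispute. The open question is which patients enter the count: one removal of this kind, if judged treatment-related, uses one of the 4 in 12 or one of the 6 in 26.

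**The case against.** **Different decisions may have different bars.** Entry, continuation and restart after toxicity are separate decisions, and a stricter bar after a Grade 3 event is coherent. That stands as a principle. It does not explain a bar that a permitted entrant did not meet on day 1, in a section that never mentions baseline although inclusion 4 does.

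**Discretion.** Section 6 leaves modifications to the investigator's judgment and says that manageable events may need none. This can avoid a hold. It gives no baseline-based way out of one, because the same paragraph sends resumption back to the table. Two sites could therefore handle identical patients differently. Footnote 13 of the Schedule of Activities relaxes eligibility values after treatment starts, but it is attached to serum chemistry and sets no resumption rule.

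**Attribution.** Table 6.1 covers events attributable to study drug. Holds for other reasons have their own restart route with approval of the overall principal investigator. A fall judged to be due to the disease is not caught. Under Section 9.4 a small laboratory change may not be an adverse event at all, and Section 5.5 allows a related event to be classed as clinically insignificant. All of this stands and makes the affected group smaller.

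**A stronger reading on DLTs.** A reader might infer that the resumption threshold inflates dose-limiting toxicities and so drives Phase 1 de-escalation, since Section 5.6 says "Any AE leading to inability to complete planned study drug during the DLT window should be considered a DLT". The documents do not support that as a general effect. Scheduled cycle 1 counts fall on dosing days 8 and 15, so a Grade 3 count found then already costs a dose whatever the resumption rule. The quoted line is printed under the nonhematologic list, so its reach to blood counts is contestable, and a DLT must be possibly related to ONC201. Only an event that is found and recovers between dosing days, as in the day 4 row, makes the threshold the sole cause.

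**Conclusion.** The concern holds in this form: the entry criteria and Table 6.1 do not fit together for patients whose listed blood count is Grade 2 at entry. In the traces, such a patient loses three or four doses and then protocol therapy, where a Grade 1 entrant with the same course loses none or one. A hold in cycle 1 also costs evaluability for response.

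This rests on four conditions: a Grade 1 lower limit above the entry floor for at least one count; a Grade 3 event attributed to study drug; a hold actually applied; and a count that stays at its entry grade for more than 21 days.

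No frequency can be given. The documents report neither the share of patients expected to enter at Grade 2 nor a rate of drug-related Grade 3 counts. Section 1.3 describes no drug-related toxicity above Grade 1 with three-weekly dosing, and no drug-related events in the early weekly-dosing patients. A reader might put assumed rates through the 3+3 design or the 4-in-12 rule and quote a higher chance of stopping, but no rate in the protocol supports such a figure. The point merits an amendment; it does not undermine the design.

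**What to change.** Reconcile Table 6.1 with inclusion 4 and 7, so that one stated resumption rule covers patients whose entry value of a listed parameter is already above Grade 1. State in Section 10.3 whether removal of a patient who is back at the entry grade counts as a treatment-related discontinuation. The sponsor and medical monitor decide what the clinical rule should be; the statistical requirement is that the passages agree and that all sites apply the same rule.

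The cost is amendment wording in Table 6.1 and Section 10.3. No visits or tests are added, because hematology is already collected at baseline and during treatment.
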